### **Treatment exposure**

- Duration of Spiriva Respimat treatment [days] = (date of last treatment intake) – (date of first intake) + 1 – (period of treatment interruption [days])  
[REDACTED]
- Total Spiriva Respimat dose taken [  $\mu$  g]

Table 5.4: 1 ICS doses of ICS product

Agent	Low dose (µg/day)	Medium dose (µg/day)	High dose (µg/day)
BDP-HFA	=< 200	> 200 to 400	> 400
FP-HFA	=< 200	> 200 to 400	> 400
CIC-HFA	=< 200	> 200 to 400	> 400
FP-DPI	=< 200	> 200 to 400	> 400
MF-DPI	=< 200	> 200 to 400	> 400
BUD-DPI	=< 400	> 400 to 800	> 800
FF-DPI		100 to <200	>= 200

BDP-HFA, beclometasone dipropionate hydrofluoroalkane;

FP-HFA, fluticasone hydrofluoroalkane; CIC-HFA, ciclesonide hydrofluoroalkane;

FP-DPI, fluticasone propionate dry powder inhaler;

MF-DPI, mometasone furoate dry powder inhaler; BUD-DPI, budesonide dry powder inhaler.

Table 5.4: 2 ICS doses of ICS/LABA combination product

Agent	Low dose (µg/day)	Medium dose (µg/day)	High dose (µg/day)
FP/SM	=< 200	> 200 to 500	> 500
BUD/FM	=< 320	> 320 to 640	> 640
FP/FM	=< 200	> 200 to 500	> 500
FF/VI		100 to <200	>= 200

FP, fluticasone propionate; SM, salmeterol xinafoate; BUD, budesonide;

FM, formoterol fumarate; FF, fluticazone furate; VI, vilanterol trifénatate.

## **6. GENERAL ANALYSIS DEFINITIONS**

### **6.1 TREATMENTS**

For basic information on treatment in the study, please refer to CTP Section 4. The technical specification for treatment set-up is described in the Analysis Data Set (ADS) plan.

For safety analyses and efficacy analyses, data up to 30 days after last treatment intake will be considered as on treatment.

### **6.2 IMPORTANT PROTOCOL VIOLATIONS**

The following table defines the different categories of important PVs. The final column describes which PVs will be used to exclude patients from the different patient analysis sets. Observed PVs will be concluded as important or not important at report planning meetings before database lock at the latest.

Table 6.2: 1 Important protocol violations

Category/Code	Description		Example/Comment	Method	Excluded from
A	Entrance criteria not met				
	A1.1	Patient received Spiriva Respimat treatment before registration	Refer to Previous Medication code:225970901	Automated	Safety
	A1.2	Patients who have been enrolled this study before		Automated	Safety
B	Contract				
	B1	No valid site contract was available		Manual	Safety
C	Trial medication				
	C1	No treatment with Spiriva Respimat		Automated	Safety
D	Missing data				
	D1	No patient visit after registration	No visit made after the entry	Automated	Safety
	D2	No CRF after registration		Automated	Safety
	D3	No safety observation was documented after registration	No AE details	Automated	Safety
	D4	No value at baseline and/or at post treatment	None of value about asthma control status, PEFR, FEV 1 , FVC and ACQ6 for efficacy analysis, at baseline and/or at post treatment	Automated	Efficacy
E	Invalid registration				
	E1	No required registration procedure was followed	See the CTP Section 9.2.2.2	Manual	Safety

[figure not shown]

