9.2.2 Selection of population

9.2.2.1 Inclusion/Exclusion criteria:

Inclusion criteria:

- Patients diagnosed with severe persistent bronchial asthmaPatient aged ≥ 15 years
- Patients who are naive to Spiriva Respimat and receive Spiriva Respimat for the first time for treatment of bronchial asthma on top of at least ICS treatment.

*:Asthma severity is defined by “Table 6 Classification of asthma severity based on the present treatment (adult)” of “Japanese Guideline for Adult Asthma 2014”[P14-15105]. Most severe persistent asthma is included in “Severe persistent asthma” indication in J-PI of Spiriva Respimat.

Exclusion criteria:

- Patients who have a contraindication to Spiriva Respimat defined in the package insert for Spiriva Respimat
- Patients who have been enrolled this study before.

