9.2.2.2 Patient registration method

The registration method will be a continuous investigation system. Patients who begin treatment with Spiriva Respimat after the conclusion of the contract will be registered by entering necessary information in the EDC within 14 days whenever possible from the day of treatment initiation (inclusive).

The necessary variable for registration is gender, date of birth, start date of administration and the reason for use. And ICS treatment as of inclusion criteria will be checked in the EDC system.

Patient registration will be stopped when the target number of the study is reached. After the end of the registration period, investigators will use a signed form to confirm that patients will be registration continuously at the site. A log of all patients included into the study will be maintained at the site.

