9.7 DATA ANALYSIS

This is a non-interventional, observational study to collect new real-world data (i.e., data under routine medical practice) on safety and effectiveness of Spiriva Respimat treatment in patients. Analyses are descriptive in nature. Due to the nature of the observational study, no confirmatory statistical testing is foreseen in this study.

Per local regulation, any patient who meets one of the following criteria is treated as ineligible for all analyses:

- No safety observation was documented after registration
- No required registration procedure was followed
- No valid site contract was available

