ANNEX 3. FLOW CHART OF VARIABLES

1. Observation period

Item	Time	Observation period ¹			
		Before first administration of Spiriva Respimat	4W	12W (or at discontinuation)	52 W (or at discontinuation)
Patient registration	X ²				
Patient demographics	X				
Administration of Spiriva Respimat	X (to be recorded throughout the observation period)				
Medical history/baseline conditions	X				
Previous/concomitant therapies	X (to be recorded throughout the observation period)				
Pulmonary function test					
FEV ₁	(X)	(X)	(X)	(X)	
FVC	(X)	(X)	(X)	(X)	
PEFR ³	(X)	(X)	(X)	(X)	
Asthma severity	X				
Asthma Control Status	(X)	(X)	(X)	(X)	
QOL (ACQ 6 score)	(X)	(X)	(X)	(X)	
Adverse events	X (to be recorded throughout the observation period)				
Laboratory tests ⁴ associated with AE	(X)				
EDC transmitted time ⁵		X		X	

(X): If applicable

1: Time points during the observation period are approximate. Collected data should be reported as of the closest available visit.

Proprietary confidential information © 2015 Boehringer Ingelheim International GmbH or one or more of its affiliated companies

- 2: Patients administered Spiriva Respimat will be registered within 14 days from whenever the day of first administration is possible.
- 3: PEFR is defined as the mean of the PEFR values of the 7 days before each visit.
- 4: When laboratory related AE is reported, Laboratory tests associated with AE are reported.
- 5: eCRF (electronic case report form): Data are to be transmitted immediately after being entered into the eCRF at 12 weeks and 52 weeks after the start of treatment or at discontinuation. In case of occurrence of any adverse events, the data should be immediately entered into the eCRF and transmitted.

APPROVAL / SIGNATURE PAGE

[figure not shown]
[figure not shown]
[figure not shown]
[figure not shown]
[figure not shown]
[figure not shown]
[figure not shown]
[figure not shown]
Document Number: c02810760

Technical Version Number: 1.0

Document Name: non-interventional-study-protocol

Title: Specific Use-Result Surveillance of Spiriva Respimat in asthmatics(patients with severe persistent asthma)

Signatures (obtained electronically)

Meaning of Signature	Signed by	Date Signed
Author-Trial Clinical Monitor		23 Apr 2015 13:19 CEST
Approval-Pharmacovigilance		23 Apr 2015 13:19 CEST
Approval-Team Member Medical Affairs		23 Apr 2015 13:27 CEST
Approval-Therapeutic Area 		23 Apr 2015 13:30 CEST
Approval-EU Qualified Person Pharmacovigilance		23 Apr 2015 13:31 CEST

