### **5.4 OTHER VARIABLES**

#### **Demographic data and baseline characteristics:**

- Sex: male, female
- Age [years]  
Age [years] = Actual age based on the first administration of Spriva Respimat  
[REDACTED]
- Height [cm]
- Weight [kg]  
[REDACTED]
- Body mass index (BMI) [ $\text{kg}/\text{m}^2$ ]  
BMI [ $\text{kg}/\text{m}^2$ ] = weight [kg] / (height [m])  
[REDACTED]
- [REDACTED]
- Smoking status: Never smoked, Ex-smoker, Current smoker, Unknown
- Pack-Years  
[REDACTED]
- [REDACTED]
- Indication for use: Bronchial asthma, Other
- Asthma Severity: Severe persistent, Moderate persistent, Mild persistent, Intermittent, Unknown

- Duration of asthma [years]  
Duration of asthma = [First administration of Spiriva Respimat – Date of indication of asthma + 1 (if negative value, then 1)] / 365.25: Day of indication is 1.  
[REDACTED]

- Number of hospital admission due to asthma in the past year (Statistics and frequency)
- Number of urgent visit to physician due to asthma in the past year (Statistics and frequency)
- Medical history: Yes, No, Unknown  
[REDACTED]

- Concomitant diagnosis: Yes, No, Unknown  
[REDACTED]

- Previous Medication: Yes, No, Unknown  
Note: Previous medications are existing drugs, drugs which administered before initiation of the new anti-asthmatic drug, drugs of unknown starting date.  
[REDACTED]

- Concomitant Medication during treatment of Spiriva Respimat: Yes, No, Unknown
  - Note: Treated during treatment period of Spiriva Respimat regardless of the start and end date of the medication (except for the case that the end date of the medication and the start date of Spiriva Respimat are the same)SABA: Yes, No, Unknown

- Concomitant therapy: Yes, No, Unknown
- Pulmonary Function Test

- Asthma control status at baseline (see the CTP Section 9.1.1.4): Well-controlled, Insufficiently-controlled, Poorly-controlled, Unknown

- Asthma symptoms (in the daytime or at night): Yes, No, Unknown
- Use of reliever: Yes, No
- Limitation of activities, including exercise: Yes, No, Unknown
- PEFR (mean of the 7 days before each visit) [L/min]
- Pregnancy test: Yes, No, Unknown
- ACQ 6 score at baseline (each score and mean of 6 questions)
- Contraindication to Spiriva Respimat: Yes, No

[REDACTED]

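### SAP exclusion D1 demands a visit after registration that Protocol 9.7 does not require, so a treated patient with a documented ADR can leave the Safety set; A1.1 is also misworded

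*SAP*

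**What the plan says.** **Exclusions.** SAP Table 6.2:1 lists D1, "No patient visit after registration", with the comment "No visit made after the entry". It is detected automatically and excludes from Safety. D2 (no CRF after registration) and D3 (no safety observation after registration) are separate codes with the same consequence. A1.1, under unmet entrance criteria, reads "Patient received Spiriva Respimat treatment before registration"; it too is automated and excludes from Safety, and its comment cell points to a Previous Medication code.

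**Analysis sets.** Protocol 9.7 makes a patient ineligible on three grounds: "No safety observation was documented after registration", registration procedure not followed, and no valid site contract. SAP 6.3 gives the same three in other words, adds that at least one dose was taken, and says that the sets are those of Protocol 9.7. SAP section 4 declares no change from the protocol.

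**Registration.** Under Protocol 9.2.2.2, patients who have begun treatment "will be registered by entering necessary information in the EDC within 14 days whenever possible from the day of treatment initiation (inclusive"). Annex 3 marks registration in the pre-dose column, but its note 2 says: "Patients administered Spiriva Respimat will be registered within 14 days from whenever the day of first administration is possible".

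**Prior use.** The inclusion criterion in Protocol 9.2.2.1 is "Patients who are naive to Spiriva Respimat and receive Spiriva Respimat for the first time for treatment of bronchial asthma". SAP 5.4 counts among previous medications "drugs which administered before initiation of the new anti-asthmatic drug".

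**Adverse events.** Collection and analysis start at first intake (Protocol 9.7.2 and 11.2, SAP 7.8.1). Protocol 9.4 has AE data entered at once when an event occurs. SAP 7.8.1 merges CRF data with data from a second AE system.

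**The concern.** A visit and a documented safety observation are different requirements. An ADR can be on record for a patient who was never seen again after registration. Protocol 9.7 keeps that patient; D1 as worded does not.

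The Safety set is the denominator of the primary outcome, and this group can include patients who react and stop early. A rule that removes people with safety data for lack of a later visit should at least be stated as a departure from the protocol. Here the SAP says that nothing has changed.

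A1.1 raises a related point. Registration normally follows the first dose, so its description fits ordinary compliant conduct, although its detection rule points elsewhere.

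**Working it through.** **1. The plan's own figure.** Protocol 9.5 enrols 360 and expects 60 to be lost with no data at all: 360 − 60 = 300, and 60/360 = 16.7%. Conversely, 300/(1 − 0.1667) = 360. This agrees with the Safety set of 300 in the Protocol Abstract. A patient whom D1 removes in addition to D2 and D3 has data, so this allowance does not cover that loss.

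**2. The rules side by side.**

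| Requirement for the Safety set | Protocol 9.7 | SAP 6.3 | Table 6.2:1 |
|---|---|---|---|
| Observation documented after registration/entry | yes | yes | D3 |
| Registration procedure followed | yes | yes | E1 |
| Valid site contract | yes | yes | B1 |
| CRF after registration | not listed | not listed | D2 |
| Visit after registration | not listed | not listed | D1 |
| No Spiriva Respimat use before registration | not listed | not listed | A1.1 |

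D2 largely follows from the first row, since without a CRF there is normally nothing documented. D1 does not.

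**3. What D1 adds to D2 and D3.** Only patients with a CRF and documented safety data but no later visit.

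- Case (a): an ADR becomes known after registration without a visit and is entered in the eCRF. Protocol 9.7 keeps this patient whether its phrase refers to when the event was observed or when it was recorded. D1 as worded removes the patient.
- Case (b): the patient reacts, stops and is last seen before registration, and the event is entered afterwards. Protocol 9.7 keeps this patient if the phrase refers to recording, the more natural reading because the registration case book (Book 1) precedes the observation book (Book 2). On the other reading, Protocol 9.7 shares the problem.

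**4. A1.1.** With the day of initiation as day 1, an on-time registration can fall on day 14, so 14 − 1 = 13 treated days can precede it. The 14 days are not a hard limit, so the gap can be longer. A patient registered after day 1 fits A1.1's description while following Protocol 9.2.2.2. The Previous Medication code, read with SAP 5.4, instead looks for use before the drug was started, which is the naive criterion.

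**5. Size per patient removed.** Let p be the ADR proportion among 300; its values are assumed, as the documents give no overall rate. Removing one ADR patient lowers it by p − (300p − 1)/299 = (1 − p)/299. Removing one event-free patient raises it by 300p/299 − p = p/299.

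| Assumed p | One ADR patient removed | One event-free patient removed |
|---|---|---|
| 1% | −0.99/299 = −0.33 pp | +0.01/299 = +0.003 pp |
| 5% | −0.95/299 = −0.32 pp | +0.05/299 = +0.017 pp |
| 10% | −0.90/299 = −0.30 pp | +0.10/299 = +0.033 pp |

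For p = 5%, 15/300 = 5.00% becomes 14/299 = 4.68%.

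**6. Direction.** If m patients are removed and k of them had an ADR, the new proportion is (300p − k)/(300 − m), which is below p only if k/m exceeds p. As an illustration, take one ADR term at 1.8%, a rate from Protocol 9.5 (5.4 expected in 300), and assume m = 10. For k = 0, 1, 2, 3 the result is 5.4/290 = 1.86%, 4.4/290 = 1.52%, 3.4/290 = 1.17% and 2.4/290 = 0.83%. Neither m nor k can be obtained from the documents.

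**The case against.** The strongest reply is that D1 is only a way of detecting that nothing was observed. Protocol 9.2.3 ties observations to scheduled time points, including one at discontinuation, and Annex 3 note 1 has data reported from the closest available visit. A patient who reacts and stops therefore has a planned observation. D1 sits with D2 and D3 under missing data. The SAP does not define a visit, so a program that accepts any visit page entered after registration could let case (b) through. Violations are also judged important or not at report planning meetings held before database lock, and the anchor to registration comes from Protocol 9.7 itself.

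Most of this stands, and it makes the group small. It does not make D1 and D3 the same rule. D3 already carries the protocol's criterion, so D1 as written has an effect only where it differs. The planning meetings classify violations; they do not align the rule with the protocol.

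Three stronger readings are tempting, and the documents do not support them.

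- That A1.1 will empty the Safety set of compliant patients. Its own check is a Previous Medication code aimed at use before initiation, so such removal is not shown.
- That D1 biases the ADR percentage downward. Step 6 shows that the direction depends on who is removed, which is unknown.
- That events in the 13 days before registration, out of the first 30-day onset band, are lost. They are not lost as such: the AE window opens at first intake, so an event on day 3 in a patient registered on day 14 and seen at week 4 is counted. The length of the gap does not measure impact.

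**Conclusion.** D1 as worded is an automated Safety exclusion that goes beyond Protocol 9.7 and SAP 6.3, and SAP section 4 does not declare it. It can remove a treated patient with a documented ADR whom the protocol keeps. The number affected is probably small and cannot be derived, and no direction of bias is established. Per ADR patient removed, the effect is a fall of 0.30 to 0.33 percentage point, assuming a Safety set of 300 and an ADR rate between 1% and 10%.

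A1.1 is a conflict between a description and its own check, with no derivable size.

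This rests on the written rule. How a visit is programmed, and whether the Analysis Data Set plan defines it, is not in the documents. The severity lies between minor and should-fix: the effect is not demonstrated, but the rule governs the primary denominator and the correction costs little.

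**What to change.** All changes are to the SAP:

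1. Delete D1, or state that any safety information from first intake onward, entered in the eCRF or the AE system, satisfies it. Either way, no patient with documented safety data is excluded for lack of a visit. Confirm with the sponsor that this is how Protocol 9.7 is meant to be read.
2. Reword A1.1 as use of Spiriva Respimat before the first administration recorded at registration, so that the description matches its Previous Medication check.
3. Align SAP 6.3 with Table 6.2:1. Declare in SAP section 4 the exclusions that go beyond Protocol 9.7: A1.1, and D1 if it is kept. Report the number of patients excluded under each code and how many of them had an ADR.

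The cost is wording in SAP sections 4, 6.2 and 6.3, the matching programming specification and one small table, using data already planned for collection. Protocol 9.7 needs a clarification only if the sponsor says that its phrase refers to when the observation was made.

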## 6.3 PATIENT SETS ANALYSED

[figure not shown]
The following two analysis sets are defined as in CTP Section 9.7. The safety set will be the basis of all demographic, baseline and safety analyses. Efficacy analysis will be on basis of the efficacy set.

- Safety set:  
This patient set includes all patients who were documented to have taken at least one dose of Spiriva Respimat except for patients who had no observation documented after entry, made invalid registration or were not under the appropriate site contact.

- **Efficacy set:**

This patient set is a subset of the safety set that includes all patients in the safety set who have baseline and at least one available on-treatment asthma control status, PEFR, FEV1, FVC or ACQ 6 score.

## **6.5 POOLING OF CENTRES**

This section is not applicable because centre/country is not included in the statistical model.

## **6.6 HANDLING OF MISSING DATA AND OUTLIERS**

Safety:

Missing or incomplete AE dates are imputed according to BI standards (see “Handling of missing and incomplete AE dates”).[\(3\)](#)

Efficacy:

Missing efficacy data will not be imputed.

## **6.7 BASELINE, TIME WINDOWS AND CALCULATED VISITS**

With regard to efficacy and safety endpoints, the term “baseline” refers to the last observed measurement prior to administration of Spiriva Respimat.

Efficacy analyses will be performed based on calculated visits as shown in [Table 6.7: 1](#). If two or more data points of a patient fall into the same interval, the closest value to the planned day will be selected. If there are two observations which have the same difference in days to the planned day or if there are two observations on the same day, the first value will be used.

Table 6.7: 1 Baseline, time windows and calculated visits

Week label	Planned days	Time window (actual days on treatment)	
		Start	End
Baseline	0	The last observed measurement prior to administration of Spiriva Respimat	
Week 4	28	1	56
Week 12	84	57	227
Week 52/EOT	364	228	End of study

## **7. PLANNED ANALYSIS**

For End-Of-Text (EoT) tables, the set of summary statistics is: N / Mean / SD / Min / Q1 / Median / Q3 / Max.

For tables that are provided for endpoints with some extreme data, median, quartiles and percentiles should be preferred to mean, standard deviation, minimum and maximum.

Tabulations of frequencies for categorical data will include all possible categories and will display the number of observations in a category as well as the percentage (%) relative to the respective treatment group (unless otherwise specified, all patients in the respective patient set whether they have non-missing values or not). Percentages will be rounded to one decimal place. The category missing will be displayed only if there are actually missing values.

In addition, individual values on demographics, safety and effectiveness will be presented in subject data listings.

### **7.1 DEMOGRAPHIC AND OTHER BASELINE CHARACTERISTICS**

Only descriptive statistics are planned for this section of the report.

### **7.2 CONCOMITANT DISEASES AND MEDICATION**

Concomitant diseases will be coded by the latest version of Medical Dictionary for Regulatory Activities (MedDRA). Frequency of patients will be summarised by system organ class (SOC) and preferred term (PT).

Concomitant medication will be coded by latest version of “Nihon-iyakuhinshu”.

### **7.3 TREATMENT COMPLIANCE**

Compliance data is not collected in this study.

### **7.4 PRIMARY ENDPOINT(S)**

The analysis of the primary endpoint is described in [Section 7.8.1](#).

## **7.5 SECONDARY ENDPOINTS**

Effectiveness at each visit in each patient is determined based on the change of asthma control status from baseline. See the assessment table for effectiveness and the CTP Section 9.1.1.4. And it will be performed as well as [Section 5.4](#). Calculate worse odds ratio in each patient characteristic (demographic and existing treatment factor).

Table 7.5: 1 Assessment table for effectiveness

	Well controlled at baseline	Insufficiently-controlled at baseline	Poorly-controlled at baseline
Well controlled after administration	Improvement	Improvement	Improvement
Insufficiently-controlled after administration	Worse	Worse	Improvement
Poorly-controlled after administration	Worse	Worse	Worse

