9.1.1.2 Secondary outcome

- Change from baseline in asthma control status at Week 52

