9.1.1.4 Assessment of effectiveness

Asthma control status:

Asthma control status will be assessed based on the “Asthma prevention and management guideline” [[! "#\\$%"&%](#)

9.1.1.4: 1 Asthma control status Table

Patients control status	Well-controlled	Insufficiently-controlled	Poorly-controlled
	Meet all the criteria	Meet 1 or 2 criteria	Meet all of 3 Criteria
Asthma symptoms (in the daytime or at night)	None	Once or more a week	Once or more a week
Use of reliever	None	Once or more a week	Once or more a week
Limitation of activities, including exercise	None	Restricted	Restricted

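### SAP Table 7.5:1 has no unchanged category, so patients whose asthma control does not change are counted as worse or as improved

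*SAP*

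**What the plan says.** Protocol 9.1.1.2 names the secondary effectiveness outcome: "Change from baseline in asthma control status at Week 52". Protocol 9.1.1.4 defines three ordered states from three criteria (symptoms, reliever use, limitation of activities). The middle state, insufficiently controlled, is defined as "Meet 1 or 2 criteria". The protocol gives no rule for turning a pair of states into improvement or worsening.

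The SAP supplies that rule in Section 7.5: "Effectiveness at each visit in each patient is determined based on the change of asthma control status from baseline". The columns of Table 7.5:1 are baseline well, insufficiently and poorly controlled, in that order. Its rows read:

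- "Well controlled after administration Improvement Improvement Improvement"
- "Insufficiently-controlled after administration Worse Worse Improvement"
- "Poorly-controlled after administration Worse Worse Worse"

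The same section then uses the *Worse* label as the outcome of a subgroup analysis: "Calculate worse odds ratio in each patient characteristic (demographic and existing treatment factor". It refers to SAP 5.4 in general terms, and 5.4 lists "Asthma control status at baseline (see the CTP Section 9.1.1.4): Well-controlled, Insufficiently-controlled, Poorly-controlled, Unknown" among the baseline variables. Section 7.5 mentions neither stratification by baseline control nor adjustment for it.

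**The concern.** An outcome described as change from baseline needs somewhere to put patients who do not change. The table has no such place. Patients who stay insufficiently or poorly controlled are reported as worse on the drug, and patients who stay well controlled are reported as improved.

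The analysis is descriptive, so these percentages are themselves the result; no test or model stands between the label and the reader. This is the only secondary outcome in the visible protocol text. Under Protocol 12 the final report goes into the re-examination documents and is the basis for a planned publication.

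The odds ratios raise a second problem. A stable patient's label depends only on baseline state, so a subgroup with fewer well-controlled patients at baseline will tend to show more *Worse*, even if its course on treatment is the same.

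**Working it through.** **1. Cell by cell.** Each label against the direction of movement:

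| Baseline | After | True direction | Table label |
|---|---|---|---|
| Well | Well | none | Improvement |
| Well | Insufficient | worse | Worse |
| Well | Poor | worse | Worse |
| Insufficient | Well | better | Improvement |
| Insufficient | Insufficient | none | Worse |
| Insufficient | Poor | worse | Worse |
| Poor | Well | better | Improvement |
| Poor | Insufficient | better | Improvement |
| Poor | Poor | none | Worse |

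By direction there are 3 improved, 3 unchanged and 3 worsened cells. The table has 4 *Improvement* and 5 *Worse*. All six off-diagonal cells are right; all three diagonal cells are labelled as change.

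**2. What follows for any data.**
- Reported *Worse* minus true worsening = share insufficient-to-insufficient + share poor-to-poor.
- Reported *Improvement* minus true improvement = share well-to-well.

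The SAP states no figure to reproduce, and the documents give no distribution of control status. Every input below is assumed.

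**3. Nobody changes category (a limiting case).** Reported *Worse* = 1 − P(well at baseline). With 0%, 10% and 20% well controlled this is 100%, 90% and 80%. Among the protocol's planned 300 patients, if all were evaluable, that is 300, 270 and 240. True worsening and true improvement are both 0%.

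**4. A mixed case.** Group A: baseline 10% well, 50% insufficient, 40% poor. Transitions:
- Well: 80% stay, 20% drop one category.
- Insufficient: 40% improve, 50% stay, 10% worsen.
- Poor: 50% improve, 50% stay.

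Results:
- True improved: 0.5×0.4 + 0.4×0.5 = 0.40.
- True worsened: 0.1×0.2 + 0.5×0.1 = 0.07.
- True unchanged: 0.1×0.8 + 0.5×0.5 + 0.4×0.5 = 0.53.
- Labelled *Improvement*: 0.40 + 0.08 = 0.48.
- Labelled *Worse*: 0.07 + 0.25 + 0.20 = 0.52.

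**5. Sensitivity to how many stay put.** Same baseline mix; all well-controlled patients stay well; 5% of insufficient patients worsen; a share s of the insufficient and poor groups is unchanged; the rest improve. True worsening is 0.5×0.05 = 2.5%. Reported *Worse* is 0.5(s + 0.05) + 0.4s = 0.9s + 0.025, which gives 29.5%, 47.5% and 65.5% for s = 0.3, 0.5 and 0.7.

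**6. Odds ratios for *Worse*.**
- No change in either subgroup, 10% against 30% well controlled: (0.9/0.1)/(0.7/0.3) = 3.86.
- Group A against Group B (baseline 30/40/30), both with the step 4 transitions. B labelled *Worse*: 0.3×0.2 + 0.4×0.6 + 0.3×0.5 = 0.06 + 0.24 + 0.15 = 0.45. OR = (0.52/0.48)/(0.45/0.55) = 1.32. Within every baseline category the OR is 1.

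**7. Would correct labels alone be enough?** For B, true improved = 0.4×0.4 + 0.3×0.5 = 0.31 and true worsened = 0.06 + 0.4×0.1 = 0.10.
- Not improved against improved, patients not well controlled at baseline: A 0.50/0.40, B 0.39/0.31; OR = 1.250/1.258 = 0.99.
- Worsened against not worsened, patients not poorly controlled at baseline: A 0.07/0.53, B 0.10/0.60; OR = 0.132/0.167 = 0.79.

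Restriction nearly removes the artefact for the first outcome here but not for the second, so baseline control still has to be accounted for.

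**The case against.** The strongest reply is that this is a success/failure rule under poor labels. The table is an assessment of effectiveness. For an add-on drug in patients with symptoms, no gain can reasonably count as failure, and a patient already well controlled can only keep that status. On that reading the step 4 discrepancy is 8 percentage points: 48% reported success against 40% truly improved, all from well-to-well patients. The reading is coherent, but neither document states it. Section 7.5 describes change from baseline, and poor-to-poor would then be not effective rather than *Worse*.

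Other points stand in part:

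- Among patients insufficiently or poorly controlled at baseline, *Worse* already equals not improved. An odds ratio of not improved against improved in those patients changes only the label and drops the well-controlled column. That is correct, but step 7 shows that dropping this column matters.
- Any unadjusted odds ratio can vary with baseline mix. Also correct, as the 0.79 in step 7 shows; it supports accounting for baseline control.
- The reference to SAP 5.4 may mean that results will be shown by baseline status. The wording is unclear, and such a display would still leave stable and deteriorating patients mixed in the insufficient column.
- A shift table may lie in a section that is not visible, and individual values are listed (SAP 7). Neither would correct the table or its odds ratios.
- A patient who goes from two criteria to one stays insufficiently controlled and is coded *Worse*. The width of that category comes from the protocol, and recoding would make this patient *Unchanged*, not improved. The recode removes the false label but does not recover the gain.

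**Conclusion.** The concern holds. Followed exactly, the plan would report stable patients as worse or improved in an outcome it describes as change from baseline, and would carry this into the odds ratios. The direction of the error is certain, because it follows from the table alone. Its size is not known: 52% *Worse* against a true 7%, and odds ratios of 1.32 and 3.86 where the true within-category value is 1, all rest on assumed baseline mixes and transitions. Control status is collected only if available, so the number evaluable may be below 300.

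The reach is limited. There is no primary effectiveness outcome, no confirmatory test is planned, and the primary safety outcome does not use this table. It should be corrected because the reported percentages would otherwise mislead on the secondary effectiveness outcome.

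**What to change.** 1. In Table 7.5:1, label the three diagonal cells *Unchanged*, and report Improved / Unchanged / Worsened.
2. Present the 3x3 table of baseline by Week 52 control status, if it is not already planned in a section that is not visible.
3. Calculate the odds ratios on an outcome whose name matches its content: for example, not improved against improved among patients not well controlled at baseline, or worsened against not worsened among patients not poorly controlled at baseline.
4. Stratify these odds ratios by baseline control status, or adjust for it; SAP 5.4 already lists the variable.
5. If a success/failure rule is intended, say so, give the reason, and name the categories accordingly, alongside the three-way report.

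The cost is one derivation rule and some SAP wording; no new data are needed. The share reported as improved falls by the well-to-well patients. Restricting the odds ratios to patients who can improve, or who can worsen, reduces the number analysed and widens the intervals.
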